## 7. PLANNED ANALYSIS

Continuous variables will be summarized as mean value with standard deviation (SD) and median, Q1, Q3, along with minimum and maximum values. The minimum and maximum values will have the precision of the data reported; mean, median values will have one additional decimal, whereas SD will have two additional decimals.

Tabulations of frequencies for categorical data will include all possible categories and will display the number of observations in a category as well as the percentage (%) relative to all subjects with non missing values for the specific variable. The category missing will be displayed only if there are actually missing values. The precision of percentages will be set at one decimal points unless the resulting output indicates point to 0.0%; in that case a second decimal will be included.

Any statistical inference will be based at 2-sided level of significance of  $\alpha=0.05$  (i.e. 95% confidence interval will be calculated).

### 7.1 DEMOGRAPHIC AND OTHER BASELINE CHARACTERISTICS

Only descriptive statistics are planned for this section of the report based on the total population (no subgroups).

The demographic and baseline characteristics described in [Section 5.4.1](#) will be summarized.

### 7.2 CONCOMITANT DISEASES AND MEDICATION

As concomitant medication is considered as any treatment received after the enrollment to the study irrespective when it was initiated (before or during the study). Concomitant medication will be presented based on ATC coding of the World Health Organization Drug Dictionary (WHO-DD) using the most recent version at the time of the database lock.

Any comorbidity reported which started prior to the study enrollment will be summarized as medical history. Separate table will summarize all comorbidities reported in the study.

### 7.3 TREATMENT COMPLIANCE

Treatment compliance is assessed secondary objective of the study and it is described in [Section 7.5.2.4](#).

### 7.4 PRIMARY ENDPOINT(S)

#### 7.4.1 Primary analysis of the primary endpoint(s)

The SGRQ Total score and the corresponding sub domains will be calculated; it summarizes the impact of the disease on the overall health status. Scores are expressed as a percentage of

overall impairment where 100 represents worst possible health status and 0 indicates best possible health status.

The primary endpoint of SGRQ Total score and the corresponding sub domains will be summarized descriptively as continuous variables at each study visit in the TS population.

The SGRQ scores to be displayed in the above mentioned summaries will be the observed values at each visit and the absolute change from baseline at each visit.

Calculation of SGRQ score for each patient is performed on patient level based on the questionnaire manual.

Change from baseline is defined as post baseline – baseline value, assuming that both time points are non missing.

Baseline value: SGRQ following to ICF signature, see [Table 6.7:1](#).

Post baseline value: Any SGRQ score after the baseline visit.

For the statistical inference regarding the SGRQ Total score and the corresponding sub domains, mixed models for repeated measurements model (MMRM) assuming random missingness will be fit. The dependent variable will be the SGRQ (Total score or the corresponding subdomains) at each visit. Visit, GAPBSL stage, FVCBSL (cut off  $\leq 70\%$ ), DLCOBSL (cut off  $< 40\%$ ) and number of comorbidities (as dictated by the medical history page) will be entered as fixed factors, baseline score by visit as interaction term.

Patients will be fitted at random and an unstructured correlation matrix will be used, allowing adjustment for correlations between study visits within the study patients. The Kenward-Roger degrees of freedom approximation will be used in the model (ddfm=kr). In case of no convergence, the following steps will be considered:

- The value used in the model as tolerance in checking singularity should be changed to 10-10 (the default value is 10-12).
- Increase the number of convergence iterations to 200 (default is 100 iterations).
- Apply scoring algorithm. Request to use the Fisher scoring algorithm up to the 4th iteration. The default is 1.
- Use a simpler covariance matrix: Should none of the previous methods does not work, the covariance matrix will be changed from unstructured to Toeplitz with heterogeneous variances. Should this also not converge, a standard Toeplitz matrix will be fitted. Finally, if convergence still does not occur, then an order-1 autoregressive matrix (AR(1)) can be fitted.

Summaries of the estimated mean change from baseline of SGRQ scores until months 3, 6, 9 and 12 will be provided with 95% confidence interval. Model information will be provided as footnote under the corresponding table.

Worth to note, that the response to incorrectly translated question 17 will be set to missing for any analysis mentioned above in all patients prior to the approval receipt date as mentioned in [Table 9.1:1](#).

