## **9.5 STUDY SIZE**

This observational study will be analyzed descriptively following standard statistical and epidemiological methods. Approximately 240 patients are expected to be included in the study in a consecutive manner between February 2019 and February 2022 from the participating sites according to the feasibility procedure of the sites. The number of included patients as well as the duration of the study is not defined by a formal sample size and power calculation, but is based mainly on the availability of eligible IPF patients as well as patient population in the selected sites.

Table 3 describes expected 95% confidence limits and precision of the estimate of mean change from baseline of SGRQ Total Score at week 52, according to different assumption of mean

change from baseline and standard deviation (SD). Sample size is assumed to be 200 because it is expected that some patients discontinue nintedanib treatment prior to the follow-up period completion.

Because SD is unknown at the planning stage, it needs to be assumed based on the previous trials. In INPULSIS trials, the sample standard deviation of the change from baseline in SGRQ total score at Week 52 was about 16. In the real-world setting, the more diverse patients are expected compared to patients in INPULSIS trials. Therefore, we assume that SD may range from 16 to 22. These calculations are based on a total number of 200 evaluable study participants. Taking into account an approximate dropout rate of 17-20%, a final number of 240 patients will be enrolled in the study.

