### **6.2 IMPORTANT PROTOCOL DEVIATIONS**

Table 6.2:1 Important protocol deviations

Category/ Code	Description	Requirements	Excluded from
A	Entrance criteria not met		
A1.1	Inclusion criteria not met as specified in the protocol:	
The following inclusion criteria not met
 
 
• Patients <math>\geq 40</math> years of age.
 
• Treatment naïve patients with initial IPF diagnosis no more than 3 months prior to enrolment according to 2011 ATS/ERS/JRS/ALAT guidelines who are initiating treatment with Nintedanib (as monotherapy for IPF) or have initiated treatment with Nintedanib (as monotherapy for IPF) within the past 7 days prior to the enrolment.*
 
• Patients for whom the decision to prescribe therapy with Nintedanib according to the locally approved product's SmPC has already been taken prior to the study enrolment and is clearly separated from the physician's decision to include patient in the current study. *
 
• Patients that are able to read, understand and complete the study specific questionnaires. *
 
	PPS
A2	Exclusion criteria met		PPS
B	Informed consent		
B1	Informed consent not available/not done	Informed consent date missing	TS, PPS
B2	Informed consent too late	Informed consent date <actual consent date> was after Visit 2 date <Visit 2 date>	
D	Concomitant medication		
D2	Prohibited medication use	Pirfenidone taken.*	PPS
D3	Mandatory medication not taken	Nintedanib treatment was not taken or interrupted	PPS

Category/ Code	Description	Requirements	Excluded from
		for 28 days period*	
E	Certain Violations of procedures used to measure primary data		
E1	Protocol amendment / incorrect CRF, implemented after the approvals and/or PI signature	Incorrected (old) version of SGRQ questionnaire is completed after the IRB approvals*	PPS
F	Certain Violations of time schedule to measure primary data		
F1	No follow-up visits performed	Only baseline visit is recorded	PPS

Note: (\*) not programming activity checks. These IPV definitions in the TSAP should be made available to the Local Clinical Monitors (CMLs)/Clinical Research Associates (CRAs) to view so they know which IPVs are programmed and hence do not need to be identified at a site level on the manual PV log.”

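### In this one-arm study, an SGRQ change interval that treats the baseline mean as fixed is too narrow for the target population and rests on a different variance from Table 3

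*SAP*

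**What the plan says.** **Model.** In SAP 7.4.1, "The dependent variable will be the SGRQ (Total score or the corresponding subdomains) at each visit". The explanatory terms are visit, baseline GAP stage, FVC and DLCO categories, number of comorbidities, and baseline score by visit. The output is a change: "Summaries of the estimated mean change from baseline of SGRQ scores until months 3, 6, 9 and 12 will be provided with 95% confidence interval". The SAP does not say how a change is derived from a model of scores, at which baseline value or factor weights it is evaluated, or whether the variance of the baseline mean enters the interval. SAP 7.5.2.1 to 7.5.2.3 use the same model form for mMRC, Cough-VAS and GAD-7.

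**Design and level.** There is one treated cohort (Protocol 9.1, SAP 6.1). SAP section 7 states: "Any statistical inference will be based at 2-sided level of significance of" 0.05, with 95% intervals.

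**Planned precision.** In Protocol 9.5, "Table 3 describes expected 95% confidence limits and precision of the estimate of mean change from baseline of SGRQ Total Score at week 52". The basis is "These calculations are based on a total number of 200 evaluable study participants". For the earlier trials, "the sample standard deviation of the change from baseline in SGRQ total score at Week 52 was about 16"; the protocol continues: "Therefore, we assume that SD may range from 16 to 22".

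**Analysis set.** SAP 6.3 makes the Treated Set primary. In SAP Table 6.2:1, code F1 ("Only baseline visit is recorded") leads to exclusion from the Per Protocol Set only.

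**The concern.** Baseline adjustment is routine in two-arm trials because the quantity of interest is a difference between arms, and the error in the baseline mean drops out of it. Here the quantity is follow-up mean minus baseline mean in a single group. The baseline mean is itself an estimate, and its sampling error belongs in the interval. A model that conditions on baseline gives a standard error for the follow-up mean at a given baseline value. Subtracting that value as a constant adds nothing for the uncertainty in the baseline mean.

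No hypothesis test is planned, so this interval is the main inferential result for the primary endpoint. Protocol 9.1 and 9.2.2 present the cohort as representing IPF patients in Greece. If the interval is read that way, it will look more precise than the data allow.

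Separately, a model with only post-baseline responses cannot use a treated patient who has a baseline SGRQ and nothing later, although the Treated Set includes that patient.

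**Working it through.** **1. Reproduce Table 3.** Inputs from Protocol 9.5: n = 200, SD of change 16 to 22, 95% interval.

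Width = 2 × 1.96 × SD_change / √200

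- SD 16: 4.43; SD 18: 4.99; SD 20: 5.54; SD 22: 6.10
- Table 3 prints 4.4, 5.0, 5.5 and 6.1, so it reproduces. Its variance is that of the change score, which includes baseline variation.

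**2. Compare the variances.** Let X be baseline, Y the month-12 score, b the slope of Y on X, s_e the residual SD and s_X the SD of X. With complete data the mean change is Ȳ − X̄.

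- Full variance: [s_e² + (1−b)²·s_X²]/n = SD_change²/n
- Variance with the baseline mean fixed: s_e²/n
- Omitted: (1−b)²·s_X²/n, which is zero only if b = 1

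Using change as the response, with the same baseline terms, shifts the slope to b − 1 but leaves s_e, and so the standard error, unchanged.

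**3. Size with equal score SDs (s) at both times.** The documents give neither s nor the correlation r, so s is assumed.

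- r = 1 − SD_change²/(2s²), and b = r
- Width ratio = √((1+r)/2)
- Coverage = 2Φ(1.96 × ratio) − 1

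Worked case, SD of change 16 and s = 20: r = 1 − 256/800 = 0.68, so s_e² = (1 − 0.68²) × 400 = 215.04. The omitted part is 0.32² × 400 = 40.96. The sum is 256 = 16². Ratio = √0.84 = 0.917.

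| SD of change | s (assumed) | r | Ratio | Width, baseline fixed | Width, Table 3 basis | Coverage |
|---|---|---|---|---|---|---|
| 16 | 18 | 0.605 | 0.896 | 3.97 | 4.43 | 92.1% |
| 16 | 20 | 0.680 | 0.917 | 4.06 | 4.43 | 92.8% |
| 16 | 25 | 0.795 | 0.947 | 4.20 | 4.43 | 93.7% |
| 22 | 18 | 0.253 | 0.792 | 4.83 | 6.10 | 87.9% |
| 22 | 20 | 0.395 | 0.835 | 5.09 | 6.10 | 89.8% |
| 22 | 25 | 0.613 | 0.898 | 5.48 | 6.10 | 92.2% |

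Simulation at n = 200 and s = 20 (4,000 runs per setting) agrees. The baseline-fixed interval had width 4.09 and coverage 92.5% at SD 16, and 5.12 and 90.1% at SD 22. The plain change-score interval covered 95% in both.

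**4. Size with the slope set directly.** SD of change 16, baseline SD 20 (assumed):

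| b | Width | Coverage |
|---|---|---|
| 1.0 | 4.43 | 95.0% |
| 0.9 | 4.40 | 94.8% |
| 0.8 | 4.29 | 94.2% |
| 0.7 | 4.11 | 93.1% |
| 0.6 | 3.84 | 91.0% |

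At b = 0.9 the loss is about 1%.

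**5. Factor weights.** GAP stage, FVC, DLCO and comorbidity count were added with assumed category splits and no true effects (s = 20). Averaging over the observed distribution gave widths 4.09 and 5.12 at SDs 16 and 22, with coverage 93.0% and 88.9%. Weighting categories equally gave 5.80 and 7.29, wider than Table 3, yet coverage was still only 93.5% and 92.7%. The unstated evaluation point therefore matters too.

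**6. Could the model's visits include baseline?** That does not help, because baseline would then be both a response and its own covariate.

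**The case against.** The strongest reply is that the SAP never says the baseline mean is a known constant; it leaves the step from score to change undefined. That stands, and it is why the point is conditional. But usual adjusted means from this model, minus a baseline mean, behave as computed above, and nothing in the SAP tells the analyst to do otherwise.

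The size is not documented, and that also stands. The lowest coverages pair a large SD of change with a modest score SD. Protocol 9.5 justifies the larger SD by a more varied population, which could raise the score SD as well. Scaling both (22 with 27.5) keeps r = 0.68, giving width 5.59 against 6.10 and coverage 92.8%.

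The interval is valid conditional on the observed baselines. That is correct, but the protocol's target is wider than the enrolled patients.

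The stakes are limited. Protocol 9.7.1 calls the analysis exploratory and descriptive, and 9.9 disclaims definite conclusions. The SAP also asks for observed change with mean and SD at each visit, so a reader could compute a paired interval for patients with both scores. Redacted SAP entries near 7.4.1 may hold further analyses. These facts lower the severity. They do not correct the model-based interval, which the SAP itself places under statistical inference.

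**Conclusion.** The point holds: an interval from the SAP 7.4.1 model with the baseline mean treated as fixed omits (1−b)²·s_X²/n and under-covers the population mean change unless b = 1. The direction is certain for complete data with averaging over the observed factor distribution. The size depends on assumed values: coverage about 92–94% at SD of change 16 and 88–92% at 22 for equal score SDs of 18 to 25, and almost no loss at b of about 0.9 or above. It should be corrected, but it does not threaten the study.

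A reader might infer two stronger things that the documents do not support.

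- **That Table 3 is wrong.** Its arithmetic reproduces. It is a planning illustration, and the mismatch is one of variance basis.
- **That leaving out baseline-only patients biases the estimated change.** No section prescribes predicting at one baseline mean and subtracting another. In simulations with a true change of 3.5, about 16% total loss driven by the last score and 4% lost before the first follow-up, using the Treated Set mean for both steps gave about 3.5; using the analysed patients' mean for both gave about 3.7. What remains is that these patients contribute nothing to the fit.

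**What to change.** In SAP 7.4.1, analyse SGRQ at baseline and months 3, 6, 9 and 12 as five repeated responses, with visit as fixed effect and a 5×5 unstructured within-patient matrix. Report the four visit-minus-baseline contrasts with 95% intervals. With complete data at n = 200 this returns the Table 3 widths (4.4 at SD 16, 6.1 at SD 22) and about 95% coverage. It also lets Treated Set patients with only a baseline score contribute.

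Decide explicitly about GAP stage, FVC, DLCO and comorbidities:

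- If they are kept to support missing-at-random, enter them with visit interactions. Evaluate the contrasts at their observed Treated Set distribution, and include the sampling variation of those means in the interval.
- If they are dropped, state that missing-at-random no longer conditions on them.

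Make the same change in SAP 7.5.2.1 to 7.5.2.3 for mMRC, Cough-VAS and GAD-7.

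The cost is SAP wording and somewhat wider intervals, with no new data. From the ratios in the table for equal score SDs of 18 to 25, the widening is about 6–12% at SD of change 16 (1/0.947 to 1/0.896) and 11–26% at 22 (1/0.898 to 1/0.792), and close to zero if the slope is near 1.

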7.1.1. Does the protocol address confounding by indication if applicable?				
7.2 Does the protocol address:				
7.2.1. Selection biases (e.g. healthy user bias)				9.2.2

Section 7: Bias	Yes	No	N/A	Section Number
7.2.2. Information biases (e.g. misclassification of exposure and endpoints, time-related bias)				9.2.2
7.3 Does the protocol address the validity of the study covariates?				

Comments:

No confounders or effect modifiers are discussed since no hypothesis testing or assessment of effects is being performed.

Section 8: Effect modification	Yes	No	N/A	Section Number
8.1 Does the protocol address effect modifiers? (e.g. collection of data on known effect modifiers, sub-group analyses, anticipated direction of effect)				

Comments:

Section 9: Data sources	Yes	No	N/A	Section Number
9.1 Does the protocol describe the data source(s) used in the study for the ascertainment of:				
9.1.1 Exposure? (e.g. pharmacy dispensing, general practice prescribing, claims data, self-report, face-to-face interview)				9.3.1, 9.4

Section 9: Data sources	Yes	No	N/A	Section Number
9.1.2 Outcomes? (e.g. clinical records, laboratory markers or values, claims data, self-report, patient interview including scales and questionnaires, vital statistics)				9.3.2, 9.4
9.1.3 Covariates?				9.3.3, 9.4
9.2 Does the protocol describe the information available from the data source(s) on:				

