## 2. LIST OF ABBREVIATIONS

Term	Definition / description
AE	Adverse Event
ATC	Anatomic Therapeutic Classification System
BAL	Bronchoalveolar Lavage
BSL	Baseline
CAD	Coronary Artery Disease
CTP	Clinical Trial Protocol
CTR	Clinical Trial Report
CV	Cardiovascular
DL CO	Diffusing Capacity for Carbon Monoxide
FAS	Full Analysis Set
FEV 1	Forced Expiratory Volume
FVC	Forced Vital Capacity
FU	Follow Up
GAD-7	Generalized Anxiety Disorder Screener Questionnaire
GAP	gender (G), age (A) and two lung physiology variables (P)
HRCT	High Resolution Computer Tomography
HRQoL	Health Related Quality of Life
ICF	Inform Consent Form
ICH	International Conference On Harmonisation
IPF	Idiopathic Pulmonary Fibrosis
LTOT	Long Term Oxygen Therapy
MedDRA	Medical Dictionary For Regulatory Activities
mMRC	modified Medical Research Council scale
MMRM	Mixed Models for Repeated Measures
PPS	Per Protocol Set
PT	Preferred Term
PD	Protocol Deviation
SD	Standard Deviation
SGRQ	St. George's Respiratory Questionnaire
sMAQ	Simplified Medication Adherence Questionnaire
SAE	Serious Adverse Event
SOC	System Organ Class
TLC	Total Lung Capacity
ToC	Table of Contents
TS	Treated Set
TSAP	Trial Statistical Analysis Plan
UIP	Usual Interstitial Pneumonia
VAS	Visual Analogue Scale

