### **3. INTRODUCTION**

As per ICH E9 (1), the purpose of this document is to provide a more technical and detailed elaboration of the principal features of the analysis described in the protocol, and to include detailed procedures for executing the statistical analysis of the primary and secondary variables and other data.

This TSAP assumes familiarity with the Clinical Trial Protocol (CTP). In particular, the TSAP is based on the planned analysis specification as written in CTP Section 9.7 “Data Analysis”. Therefore, TSAP readers may consult the CTP for more background information on the study, e.g., on study objectives, study design and population, treatments, definition of measurements and variables, planning of sample size. SPSS Version 24 will be used for all analyses.

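### The SAP does not say how the single-arm MMRM averages over its covariate factors; with equal level weights, the mean change would not describe the treated cohort and its interval would be wider than Table 3 suggests

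*SAP*

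**What the plan says.** SAP 7.4.1 models the SGRQ score (total or domain) at each visit, not the change. Visit, GAP stage, FVC (cut at 70%), DLCO (cut at 40%) and "number of comorbidities (as dictated by the medical history page) will be entered as fixed factors, baseline score by visit as interaction term". No factor-by-visit terms are listed. The output is described only as follows: "Summaries of the estimated mean change from baseline of SGRQ scores until months 3, 6, 9 and 12 will be provided", with a 95% confidence interval. SAP 7.5.2.1 to 7.5.2.3 repeat the model for mMRC, Cough-VAS and GAD-7.

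The visible text does not give the weights for averaging over factor levels, say whether the comorbidity count is grouped, or explain how a change is obtained from a model of the score. On software, SAP 3 says only "SPSS Version 24 will be used for all analyses". The SAP abbreviation list expands GAP as "gender (G), age (A) and two lung physiology variables (P"), so lung physiology enters both through GAP and through the FVC and DLCO classes.

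Table 3 in Protocol 9.5 plans precision for the plain mean change at week 52. The primary endpoint (Protocol 9.3.2.1) is the mean change in patients treated with nintedanib.

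**The concern.** In a two-arm trial, the weights given to main-effect covariates drop out of the treatment contrast. Here the visit mean is itself the result, so the weights are part of what is estimated. An analyst who requests marginal means without a weighting instruction will usually get equal weights: one third to each GAP stage, one half to each FVC and DLCO class, and the same weight to a comorbidity count held by one patient as to one held by fifty. Because GAP overlaps with FVC and DLCO, some of the combinations averaged over will be nearly empty.

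Two things are at stake. The model estimate may refer to a population other than the treated cohort, and sparse levels may widen its interval for no gain. Two analysts could follow the visible SAP exactly and report different primary estimates.

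**Working it through.** **1. Reproduce Table 3.** The inputs are N = 200 (Protocol 9.5: "These calculations are based on a total number of 200 evaluable study participants"), SD = 16 ("In INPULSIS trials, the sample standard deviation of the change from baseline in SGRQ total score at Week 52 was about 16") and two-sided alpha 0.05 (SAP 7).

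Width = 2 × 1.96 × SD/√N = 2 × 1.96 × 16/√200 = 4.43. With SD 22 it is 6.10. Table 3 prints 4.4 and 6.1, so it plans the unadjusted mean.

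**2. Why the weights stay.** The model mean at visit v is (visit effect) + Σ wⱼγⱼ + (baseline term), where γⱼ are the factor-level effects and wⱼ the weights. With no second arm, nothing subtracts Σ wⱼγⱼ. Without factor-by-visit terms it is the same constant at months 3, 6, 9 and 12. It therefore moves every change from baseline equally and leaves differences between follow-up visits alone.

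**3. Precision, one factor at a time.** With level proportions pⱼ, the standard error relative to the plain mean is √(Σ wⱼ²/pⱼ). Observed weights (wⱼ = pⱼ) give √(Σ pⱼ) = 1. Equal weights over k levels give √(Σ(1/pⱼ)/k²). For assumed proportions:

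- GAP 40/45/15%: √[(2.50 + 2.22 + 6.67)/9] = 1.12.
- Comorbidity count 25/30/20/12/7/4/2%: √[(4.00 + 3.33 + 5.00 + 8.33 + 14.29 + 25.00 + 50.00)/49] = √2.24 = 1.50.

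The rarest two comorbidity levels supply 75 of the 110 in the second sum.

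**4. Precision, the four-visit model.** This is the generalised least squares variance of the month-12 mean with all four factors and baseline by visit. From the documents: 240 enrolled and SD 16. Assumed: about 210 patients at month 12, GAP about 45/45/10%, FVC ≤70% in 32%, DLCO <40% in 27%, Poisson comorbidity count with mean 1 to 4, residual correlation 0.4 to 0.8, and baseline–change correlation 0 to 0.5. Protocol 9.5 expects 17–20% dropout, which leaves 192 to 199 of 240, so every width would be slightly larger.

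| Comorbidity count | Weights | Median ratio to 4.43 | Width |
|---|---|---|---|
| Ungrouped factor | equal | 1.56–2.24 | 6.9–9.9 |
| Ungrouped, SD growing over visits | equal | 1.47–1.60 | 6.5–7.1 |
| Grouped at 3+ or 4+ | equal | 1.13–1.37 | 5.0–6.1 |
| Linear (other factors equal) | equal | about 1.1 | 4.8–4.9 |
| Ungrouped factor | observed | 0.82–0.95 | 3.6–4.2 |
| Ungrouped, 20% without FVC/DLCO | observed | 1.01 | 4.5 |

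A second four-visit calculation (N = 200, SD 16, other assumed inputs) gave widths of about 8–11 ungrouped (8/4.43 = 1.8 to 11/4.43 = 2.5), 5.3–8.3 capped or linear (1.2 to 1.9), and 4.4 at observed proportions. Together the ranges are about 1.5–2.5 ungrouped and 1.1–1.9 grouped or linear.

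**5. Point estimate.** Assume GAP 50/38/12%, scored 0, 1, 2. The cohort mean is 0.38 + 2 × 0.12 = 0.62; the equal-weight mean is 1.0; the shift is 0.38 per unit of stage gradient. A Poisson(2) count shows about 7.6 levels (0 to about 6.6), so its mean moves from 2 to about 3.3, a shift of 1.3 per unit of count gradient. With assumed gradients of 2 points per stage and 0.5 per comorbidity, the shift is 0.38 × 2 + 1.3 × 0.5 = 1.41 points, before FVC and DLCO. Month-12 simulations under assumed gradients gave 0.2 (strata nearly balanced), 1.3, 2.0 and 2.9 points. Table 3 considers total changes of 2 to 5 points, with a half-width of 2.2 at SD 16. Reversing the gradients reverses the sign.

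**The case against.** The strongest reply is that the SAP nowhere prescribes equal weights. That stands. A reader might infer that the primary estimate definitely describes an artificial, equally weighted population. The documents support only that the weighting is unspecified and that a common default would have this effect.

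The coding of GAP and of the comorbidity count may also sit in blacked-out text. The SAP contents list has redacted entries, including one directly after 7.4.1, and SAP 7.1 points to a Section 5.4.1 that is not visible. So a flat claim of twice the planned width does not stand either: it needs an ungrouped count with sparse levels. Table 3 was also never a plan for this model's interval.

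SAP 7.4.1 summarises the observed change at each visit in the treated set as well, so the plain cohort mean will be reported. This is a partial answer. SAP 7 lists no confidence interval among the continuous summaries, Protocol 9.7.1 allows one only where needed, and SAP 7.4.1 assigns inference to the model.

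Finally, a reader might take the checklist comment in Protocol Annex 2, "No confounders or effect modifiers are discussed since no hypothesis testing or assessment of effects is being performed", to mean that the covariates should go. It does not bar them, and Protocol 9.7.1 leaves modelling detail to the SAP. Follow-up ends at permanent treatment discontinuation (Protocol 9.2.4), so baseline severity terms may make the missing-at-random assumption more credible. Removing them is a debatable trade-off.

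**Conclusion.** The concern holds as a gap in specification with a material consequence under a likely default. If levels are weighted equally, the model's mean change does not refer to the treated cohort. At SD 16 its month-12 interval is then about 1.5–2.5 times 4.4 with an ungrouped count, or 1.1–1.9 times with a grouped or linear one. Observed-distribution weighting brings it to about the Table 3 width or below.

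The point estimate may shift by about 0.2 to 3 points. These sizes rest on assumed covariate distributions and gradients; none is in the documents. A reader might also infer a shift towards apparent worsening. That would need the rarer levels to be the ones that do worse, which is plausible but not documented.

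The study is exploratory and the observed means are also reported, so this is a should-fix. It affects the primary endpoint and three secondary endpoints.

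**What to change.** In SAP 7.4.1, and by reference in 7.5.2.1 to 7.5.2.3:

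- State that each visit's model mean and interval are computed at the cohort's observed covariate distribution, by mean-centring the covariates or averaging the patients' predictions.
- Enter the comorbidity count as a continuous term, or in groups fixed in advance.
- State how change from baseline, with its interval, is derived from the modelled score.

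GAP, FVC and DLCO may stay if the sponsor wants them. The cost is SAP wording and slightly more programming; no new data are needed.
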